## **4 STUDY POPULATION**

### **4.1 Source and Number of Patients**

A total of 216 patients will be randomized.

### **4.2 Patient Selection Criteria**

#### **4.2.1 Inclusion Criteria:**

All of these criteria must be met:

- Covid-19 positive by polymerase chain reaction (PCR) testing;
- Participant must be able to evaluate their symptoms and report them in the symptoms' diary;
- Patients must be able to take their oral temperature daily with an electronic thermometer provided to them with study materials;
- Males and females, at least 18 years of age, capable and willing to provide informed consent;
- Female patient is either not of childbearing potential, defined as postmenopausal for at least 1 year or surgically sterile, or is of childbearing potential and practicing at least one method of contraception and preferably two complementary forms of contraception including a barrier method (e.g. male or female condoms, spermicides, sponges, foams, jellies, diaphragm, intrauterine device (IUD)) throughout the study;
- Patient must have received a diagnosis of COVID-19 infection within the last 48 hours and have one or more symptoms;
- Outpatient setting (not currently hospitalized or under immediate consideration for hospitalization);
- Patient must be able and willing to comply with the requirements of this study protocol.

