## SYNOPSIS

**TITLE: A phase 2, randomized, double-blind, placebo-controlled study of hesperidin therapy on COVID-19 symptoms:  
The Hesperidin Coronavirus study (Hesperidin)**

**INDICATION:** Reduction of symptoms in patients with COVID-19 infection.

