**Table 1 Timetable of Visits and Procedures**

Visits	1. Screening / randomization (Phone call)	2. Contact Point (Phone) –no window**	3. Contact Point (Phone) (± 1 day)	4. Contact Point (Phone) (± 3 days)	5. Contact Point (Phone call) (± 3 days)
Days	0	3	7	10	14
Informed consent	X				
Demographics	X				
Medical/Surgical history	X				
Review concomitant medication	X	X	X	X	X
Covid-19 symptoms (including date of onset)	X	X	X	X	X
Review Inclusion/Exclusion criteria	X				
Urinary pregnancy test*	X				
Randomization	X				
Record potential study endpoints and other AEs		X	X	X	X
Study medication dispensing	X				
Study medication compliance		X	X	X	X

\*For women of childbearing potential

\*\* If day 3 occurs on the weekend, contact point will be done on previous Friday or following Monday, whichever is closer to day 3.

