## **8 DATA ANALYSIS AND STATISTICAL CONSIDERATIONS**

### **8.1 Statistical Power and Sample Size Considerations**

Sample size is based on the proportion of subjects with any of the following COVID-19 symptoms: fever, cough, shortness of breath or anosmia at day 7 since this time point will be the primary focus. Using a two-sided 0.05 significance level, sample sizes of 91 in both groups (182 total) will achieve 80% power to detect an absolute between groups difference of 20% in the proportion of subjects with the above COVID-19 symptoms at day 7. This is assuming that the proportions of patients with the above COVID-19 symptoms at day 7 will be 50% in the placebo group and 30% in the active treatment group. Factoring in a 15% drop out rate, a total of 216 patients will be randomized in the study (108 per group).

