### **8.3 Data analysis**

#### **8.3.1 Analysis of efficacy outcomes**

Efficacy analysis will be based on the intent-to-treat principle. The primary analysis will compare the proportions of subjects with fever, cough, shortness of breath or anosmia between the two treatment groups using a generalized linear mixed model with terms for treatment group (placebo, hesperidin), time (3, 7, 10 and 14 days) and treatment group x time interaction. The primary analysis will be the comparison between treatment groups at day 7, although treatment groups will also be compared at the other time points. Mean number of COVID-19 symptoms will be compared between treatment groups using a Student t-test or a Wilcoxon rank-sum test according to distribution. If more appropriate, a Poisson regression model will be used. Duration of COVID-19 symptoms will be compared between treatment groups using a log rank test and Kaplan-Meier curves will be presented. Subjects who will still have COVID-19 symptoms at the end of the study will be censored at the day of their last phone contact or videovisit. The analysis of individual COVID-19 symptoms over time will be similar to the analysis of the primary endpoint and will use generalized linear mixed models. Composite of COVID-19-related hospitalization, mechanic ventilation or death will be compared between treatment groups using a chi-square test. All statistical tests will be two-sided and conducted at the 0.05 significance level. Statistical analysis will be done using SAS version 9.4 or higher.

Full details of the statistical analysis will be described in a statistical analysis plan that will be finalized and approved prior to database lock.

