### 4 EFFICACY ENDPOINTS

#### 4.1 Primary Efficacy Endpoint

The primary endpoint will be the proportion of subjects with any of the following COVID-19 symptoms: fever, cough, shortness of breath or anosmia, at day 3, 7, 10 and 14 of the patient's symptoms diary.

Presence of these symptoms (Yes/No) will be identified using the Covid-19 Symptoms Form of the eCRF (variables COUGH, FEVER [considered a symptom if greater than 38°], SBREATH and ANOS respectively) at DAY 3, DAY 7, DAY 10 and DAY 14.

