### **6.4.1 Primary Analysis**

Number and proportion of patients with fever, cough, shortness of breath or anosmia will be summarized at 3, 7, 10 and 14 days, overall and by treatment group.

The primary analysis will compare the proportions of subjects with these symptoms between the two treatment groups using a generalized linear mixed model (GLMM), more precisely a repeated binary logistic regression model, with terms for treatment group (placebo, hesperidin), time (3, 7, 10 and 14 days) and treatment group x time interaction. Contrasts under this model will allow for the comparisons of the proportions at each time point. The primary analysis will be the comparison between treatment

groups at day 7, although treatment groups will also be compared at the other time points. Odds ratios will be provided at each time point with 95% confidence intervals and p-values.

Data for the primary endpoint will be listed.

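### Any one symptom qualifies a patient, but the primary endpoint counts only four, and the primary model ignores Day 0 status on those four although it is collected

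*Protocol*

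**What the plan says.** - **Entry.** Protocol 4.2.1 (and the Synopsis): "Patient must have received a diagnosis of COVID-19 infection within the last 48 hours and have one or more symptoms". Nothing limits which symptom. The diary in Protocol Appendix E and SAP Appendix A lists 13, so a PCR-positive patient with only a headache or runny nose qualifies.
- **Endpoint.** SAP 4.1: "proportion of subjects with any of the following COVID-19 symptoms: fever, cough, shortness of breath or anosmia", at Days 3, 7, 10 and 14. Fever counts only above 38°. Protocol 1.3 explains the choice: these are the group A symptoms, held to be less subjective and more frequent.
- **Indication.** Synopsis: "Reduction of symptoms in patients with COVID-19 infection". The primary objective is worded as an effect on the presence of the four symptoms.
- **Model.** SAP 6.4.1: a repeated binary logistic model "with terms for treatment group (placebo, hesperidin), time (3, 7, 10 and 14 days) and treatment group x time interaction", on the ITT population, with Day 7 as the primary comparison. It has no baseline symptom term, and no stratified or restricted analysis is planned.
- **Day 0 data.** The Timetable of Visits schedules "Covid-19 symptoms (including date of onset") at the screening/randomization call, and the diary instructions say symptoms will be asked about at the start of the study. The SAP uses pre-randomization symptoms only descriptively (6.3.1, Table 1.1.2).
- **Sample size.** Protocol 8.1: "sample sizes of 91 in both groups (182 total) will achieve 80% power to detect an absolute between groups difference of 20"%, with Day 7 proportions that "will be 50% in the placebo group and 30% in the active treatment group". No source is given for these rates. They are not tied to Day 0 group A status.

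**The concern.** The same endpoint asks two questions. In a patient who starts with cough, absence of group A symptoms at Day 7 means clearance. In a patient who starts with only diarrhea, it means that no group A symptom has appeared. The stated indication is about the first question. Patients of the second kind say little about clearance but count fully in both denominators, so a treatment effect that works only by clearing symptoms looks smaller in the whole group than in patients who had something to clear.

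Day 0 group A status is also likely to predict Day 7 status strongly. Leaving it out of the model gives up precision that could be had from data already being collected.

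**Working it through.** **1. The plan's own figure.** Inputs from Protocol 8.1 and 8.3.1: 50% vs 30%, two-sided 0.05, 80% power.

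- Unpooled normal approximation: n = (1.960 + 0.842)² × (0.5×0.5 + 0.3×0.7) / 0.20² = 90.3, so 91 per arm. Power at 91 is 80.3%.
- Dropout: 91 / 0.85 = 107.1, so 108 per arm and 216 in total.

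The stated figures reproduce. The pooled version of the test gives 93 per arm, and 79.1% power at 91. The comparisons below use the pooled version throughout, so 79.1% is the reference.

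**2. How large could f be?** The documents give no value for f, the share with no group A symptom at Day 0. Protocol 1.3 gives fever 83.3% (95% CI 78.4-87.7), cough 60.3% and anosmia 59% in non-hospitalized patients. Its frequency table gives shortness of breath 31-63%. Taking these as Day 0 prevalences is an assumption, because they describe reported cases.

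- Independent symptoms, without shortness of breath: 0.167 × 0.397 × 0.41 = 2.7%.
- Adding shortness of breath: 2.7% × 0.69 = 1.9%, or 2.7% × 0.37 = 1.0%.
- Complete nesting (every group A patient has fever): 1 - 0.833 = 16.7%, or 1 - 0.784 = 21.6% at the lower confidence limit.

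This gives about 1-3% under independence and up to about 17-22% under full nesting.

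**3. Dilution if 50% vs 30% applies to patients with a group A symptom.** Let q be the Day 7 rate in the other patients, equal in both arms (no preventive effect). The arm rates are (1 - f) × 0.50 + f × q and (1 - f) × 0.30 + f × q. The difference is 20 × (1 - f) points whatever q is. With q = 10% (assumed) and 91 per arm:

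| f | Placebo | Hesperidin | Difference (points) | Power, full set | Power, group A subset, 91 × (1 - f) per arm |
|---|---|---|---|---|---|
| 0 | 50.0% | 30.0% | 20.0 | 79.1% | 79.1% |
| 2% | 49.2% | 29.6% | 19.6 | 77.7% | 78.3% |
| 10% | 46.0% | 28.0% | 18.0 | 71.4% | 74.7% |
| 20% | 42.0% | 26.0% | 16.0 | 62.7% | 69.6% |

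The last column is the undiluted 50% vs 30% comparison in fewer patients. Restricting recovers 74.7 - 71.4 = 3.3 points at f = 10% and 69.6 - 62.7 = 6.9 points at f = 20%. The rest of the fall from 79.1% comes from having fewer informative patients, and no analysis recovers it.

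**4. If the drug also prevents onset.** Apply the same risk ratio, 30/50 = 0.6, to onset. With f = 20% and 20% onset on placebo (12% on hesperidin), the difference is 0.8 × 20 + 0.2 × 8 = 17.6 points and power is 70.4%. With 20% onset in both arms, power is 61.5%. Dilution is smaller but still present.

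**5. If 50% vs 30% already describes everyone enrolled.** Planned power is unchanged. The effect required among patients with a group A symptom is then 20 / (1 - f) points, with no effect in the others: 22.2 at f = 10% and 25.0 at f = 20%.

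**The case against.** The strongest counter-argument is that the endpoint is sound as defined. The primary objective concerns presence of symptoms, which covers both clearing existing ones and preventing new ones. The rationale in Protocol 1.1 and 1.2 includes blocking viral entry and replication, so fewer new coughs by Day 7 would be a genuine treatment effect. Broad entry also serves the secondary endpoints: the 0-13 count, duration and individual symptoms. And f may be only 1-3%, which costs about two points of power or less. All of this stands, and it limits the size and urgency of the point.

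A reader might infer several stronger things that the documents do not support:

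- **That patients without a group A symptom cannot respond.** They can develop one, and the drug might prevent it.
- **That the trial is undersized.** The 91 and 216 reproduce, and Protocol 8.1 does not restrict 50% vs 30% to patients with a group A symptom.
- **That power could fall to about half.** This needs f near 30%. The widest ranges in the Protocol 1.3 frequency table allow up to 43% (1 - 0.57), but only with complete nesting and every symptom at its lowest frequency. The point estimates in the same section do not support it.
- **That chance imbalance in Day 0 status biases the result.** It is ordinary random error, already in the standard error. Adjustment is about precision.
- **That Day 0 enters the primary model as an outcome.** It does not: the model's time points are 3, 7, 10 and 14 days.

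What survives is that the plan never uses a relevant baseline variable that it collects, and never separates clearance from new onset.

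**Conclusion.** The mismatch between entry and endpoint is real, and nothing elsewhere in the plan addresses it. Its size is unknown because f is not given. If 50% vs 30% refers to patients with a group A symptom, onset is 10% in both arms and the drug only clears symptoms, power falls from 79.1% to 77.7% at f = 2%, 71.4% at 10% and 62.7% at 20%. The loss is smaller if the drug also prevents onset. It is absent if the planned rates already describe the enrolled mix.

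This is an inexpensive improvement to the analysis, not a fault in the sample size or a threat to validity. A reader might go further and call for entry to be limited to patients with a group A symptom. The documents do not make that case, since broad entry serves the all-symptom secondary endpoints, so no eligibility change is recommended.

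**What to change.** Amend the SAP before database lock:

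1. **Primary model (6.4.1).** Add presence of at least one of fever, cough, shortness of breath or anosmia at Day 0 (yes/no, patient-reported at the Day 0 call) as a fixed term. State the rule for Day 0 fever. The study thermometer is delivered to the home after randomization and the diary starts at Day 1, so a reading above 38° on the study device cannot be assumed at the Day 0 call. Confirm that the eCRF records each of the four symptoms at Day 0.
2. **Supplementary analysis.** Pre-specify one Day 7 comparison, by the same method, in ITT patients with at least one group A symptom at Day 0. The subset is defined by pre-randomization status, so the comparison remains randomized. It supports the ITT primary analysis and does not replace it.
3. **Reporting.** Add the share with no group A symptom at Day 0, by arm, to SAP Table 1.1.2, so that f becomes known.

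**Cost.** SAP wording, one extra table and one extra row, with no new data collection if the eCRF check holds. The primary odds ratio becomes conditional on Day 0 status and should be labelled so. The subset has fewer patients: 74.7% power at f = 10% and 69.6% at f = 20%. If f is 1-2%, the new term rests on about 2 to 4 of 182 evaluable patients and will change little.

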#### **4.2.2 Exclusion Criteria:**

None of these exclusion criteria should be met:

- Patient currently hospitalized or under immediate consideration for hospitalization;
- Patient currently in shock or with hemodynamic instability;

- Patient undergoing chemotherapy for cancer;
- Patient is unable to take oral temperature using an electronic thermometer;
- Patient who received at least one dose of the COVID-19 vaccine;
- Female patient who is pregnant or breast-feeding or is considering becoming pregnant during the study;
- People taking anticoagulant/antiplatelet medications, those with bleeding disorders, and people two weeks before or after surgery;
- Patient is considered by the investigator, for any reason, to be an unsuitable candidate for the study;
- Regular consumption of natural products containing more than 150 mg of hesperidin or regular consumption of more than 1 glass of orange juice per day;
- Known allergy to any of the medicinal and non-medicinal ingredient: hesperidin, microcrystalline cellulose, magnesium stearate.

#### **4.3 Prohibited, Allowable and Concurrent Medications**

Clinical research suggests that hesperidin may affect blood clotting and increase the risk of bleeding. Consequently, anticoagulant and antiplatelet medications are not allowed during the study. Other medications are allowed as long as they are stabilized prior to study entry and maintained as stable throughout the course of the trial.

The use of concomitant medications at the time of randomization will be recorded in the eCRF (with the exceptions of concomitant medication taken “when necessary” (PRN)).

The use of natural products containing hesperidin and its content (in mg) as well as the quantity of orange juice consumption (in ml) will be obtained. Daily consumption of more than 150 mg of hesperidin daily or of more than one glass of orange juice daily will represent an exclusion criterion. Subjects will be encouraged to avoid hesperidin-containing supplements and orange juice for the duration of the study.

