### **3.4 Active Treatment Period**

All patients will receive study medication per os (PO) once daily for 14 days. If a dose is missed, it should not be replaced. Throughout the study, patients will undergo phone contacts (at 3, 7, 10 and days to assess for potential study endpoints and other adverse events (AEs). Patients will be dispensed study medication for the 14 days, an electronic thermometer and a daily symptoms diary. At each phone contact, patients will be 1) questioned about COVID-19 symptoms; 2) questioned in a non-specific manner for the occurrence of AEs and any change in concomitant medications; and 3) encouraged to comply with the study protocol including adherence to study medication and completion of the daily symptoms diary.

Please refer to Table 1 and Appendix A for Timetable of Visits and Procedures.

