#### **5.2.1.2 Adverse Event Follow-Up**

Record all reportable serious and non-serious AEs on the appropriate eCRF including the onset, duration, severity, relationship to the study drug, and ultimate management. All AEs reported during the treatment phase should be recorded and followed until the AE has subsided, or stabilized or until the end of the study, whichever occurs first. The study will be stopped at any time if new knowledge is gained and the risk-benefit ratio is no longer favorable for the participating patients and Ingenew Pharma will then be informed immediately but no later than 3 business days if such decision is made

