#### **4.2 Other Adverse Events**

Study endpoints are to be reported in the eCRF within 5 days of awareness of the event.

In addition to SAEs and study endpoints, the only AEs to be recorded on the eCRF are those that are judged related to the study medication by the investigator or that are laboratory abnormalities

judged clinically significant by the investigator. Information collected will include the onset, duration, severity, relationship to study drug, and the management.

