### 6.5.2 Adverse Events and Serious Adverse Events

#### 6.5.2.1 Adverse Events

AEs will be coded by system organ class and body system according to the MedDRA dictionary (version 23.1).

The total number of TEAEs reported, the number and proportion of subjects experiencing at least one TEAE, at least one severe TEAE, at least one TEAE related to the study treatment, and at least one TEAE leading to drug withdrawal will be presented. In addition, number and proportion of subjects experiencing a treatment-emergent AE will be presented by system organ class, preferred term and severity overall and for each treatment group.

All AEs will be listed but only treatment-emergent AEs will be summarized. Listing will include Subject ID, age, gender, date of beginning of treatment, name and preferred term of AE, start and stop date, severity, relationship to study drug and outcome.

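### Bleeding is a stated drug risk, but with no directed question, no consistent rule to record every bleed and no pooled summary, the trial will describe it poorly

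*Protocol*

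**What the plan says.** Protocol 4.3 states the risk: "Clinical research suggests that hesperidin may affect blood clotting and increase the risk of bleeding". It then disallows anticoagulants and antiplatelets during the study. Protocol 4.2.2 carries the matching exclusion: "People taking anticoagulant/antiplatelet medications, those with bleeding disorders, and people two weeks before or after surgery".

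On eliciting events, Protocol 3.4 says that at each phone contact patients will be "questioned in a non-specific manner for the occurrence of AEs and any change in concomitant medications". Appendix B section 1 repeats the non-specific approach. The 13-item diary in Appendix E has no bleeding or bruising item, only a free-text line for comments or other symptoms. The visit timetable contains no laboratory test other than the urine pregnancy test.

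On recording events, the documents point two ways:
- Protocol 5.2.1.2: "Record all reportable serious and non-serious AEs on the appropriate eCRF".
- SAP 5.1 describes AE collection at days 3, 7, 10 and 14 without restricting it to related events.
- Protocol Appendix B section 4.2: beyond serious events and study endpoints, "the only AEs to be recorded on the eCRF are those that are judged related to the study medication by the investigator", plus clinically significant laboratory abnormalities.

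On reporting, SAP 6.5.2.1 says the proportion of subjects with a treatment-emergent AE "will be presented by system organ class, preferred term and severity overall and for each treatment group". It adds: "All AEs will be listed but only treatment-emergent AEs will be summarized". The table list in SAP section 7 (Tables 3.2.1 to 3.2.4) has no bleeding grouping and no event of special interest. SAP 6.5 makes safety descriptive, without testing.

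**The concern.** The protocol takes bleeding seriously enough to restrict concomitant medication and exclude patients, but the measurement plan treats it like any other event. A nosebleed or easy bruising may not be mentioned in reply to an open question. If it is mentioned and judged unrelated, Appendix B 4.2 would keep it off the eCRF. If it is recorded, it appears as one preferred term among many.

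At stake is how a quiet AE table would be read. A reader could take it as evidence of no bleeding signal when part of the information was never collected. The protocol is itself divided on the risk. Section 1.2 reports no adverse events at high doses, and the side effects listed in section 6.2 do not include bleeding, yet section 4.3 restricts medication because of it. Randomized, blinded data are a good place to describe this risk properly.

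**Working it through.** **1. The plan's own figure.** The documents give no sample size or rate for bleeding. The only calculation is for efficacy (Protocol 8.1, SAP 6.1): 50% versus 30%, two-sided 0.05, 80% power. With unpooled variance, n = (1.960 + 0.842)² × (0.25 + 0.21) / 0.20² = 90.3, so 91 per arm. With 15% dropout, 91 / 0.85 = 107.1, so 108 per arm and 216 in total. The stated figures reproduce. They fix the number available for safety: at most 108 on hesperidin, about 91 if dropout is as assumed.

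**2. What zero bleeds would exclude.** The one-sided 95% upper bound with zero events in n patients is 1 − 0.05^(1/n).
- n = 108: 2.7%.
- n = 91: 3.2%.

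If only a fraction c of bleeds reaches the database, the bound is divided by c. The documents give no value for c, so these are assumptions:

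| Capture c | n = 108 | n = 91 |
|---|---|---|
| 100% | 2.7% | 3.2% |
| 50% | 5.5% | 6.5% |
| 25% | 11% | 13% |

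**3. What under-capture does to the comparison.** Under double blinding, c should be similar in both arms. The recorded risk difference is then c times the true one. For an assumed 1% versus 5%, the true difference is 4 points; at c = 0.5 the recorded difference is 0.5 × 4 = 2 points.

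**4. The recording rules side by side.** SAP 6.5.2.1 plans separate counts of subjects with any treatment-emergent AE and with a related one. Under Appendix B 4.2, the two could differ only through serious events, endpoints and laboratory findings, because other unrelated events would not be on the eCRF. The wider reading of Protocol 5.2.1.2 and SAP 5.1 gives a different dataset. The word *reportable* in 5.2.1.2 could be read as deferring to the appendix; in that case unrelated minor bleeds are lost by rule.

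**5. What the absence of a pooled row does.** Illustration with 108 per arm (Fisher's exact test, two-sided): 6 versus 0 bleeds gives p = 0.029 as one row. The same six spread as 3 + 3 give p = 0.25 in each row; spread as 2 + 2 + 2, p = 0.50 in each. With fewer than 6 versus 0, even the pooled row does not reach 0.05.

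**6. What the trial could show with full capture and pooling.** Fisher power at 108 per arm, all rates assumed:

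| Placebo | Hesperidin | Power |
|---|---|---|
| 1% | 3% | 4% |
| 1% | 5% | 23% |
| 2% | 6% | 20% |
| 5% | 10% | 21% |
| 5% | 15% | 63% |

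For 80% power (normal approximation) the hesperidin rate would have to be about 9.5%, 12% or 17% for placebo rates of 1%, 2% or 5%.

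**The case against.** The strongest reply is that this is a legitimate design choice with safeguards. Open questioning avoids suggestion, and there are four active contacts. The diary has a free-text line. Serious bleeds and bleeds judged related are recorded. An independent DSMB reviews unblinded safety data. The phone script, the annotated CRF and the DSMB charter are not among the documents, so a directed question or a bleeding review may exist there. All of this stands, and it keeps the point minor. None of it, as documented, prompts for minor bleeds, secures the recording of those judged unrelated, or pre-specifies a pooled comparison.

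Four stronger readings are tempting and are not supported:
- *Bleeding is the only drug risk behind an exclusion.* Protocol 4.2.2 also excludes "Known allergy to any of the medicinal and non-medicinal ingredient: hesperidin, microcrystalline cellulose, magnesium stearate". Bleeding is the only pharmacological risk given as a reason.
- *Bleeds will never be added up.* The SAP does not mention bleeding terms; that bleeds at different sites fall in different organ classes is an inference from how such coding normally works. Recorded bleeds can be summed from Table 3.2.2 and Listing 7, though not as a pre-specified analysis.
- *The questioning and tables are why the trial cannot settle causality.* The power table shows that 108 per arm over 14 days is the binding limit even with perfect capture, and the plan claims only descriptive safety.
- *Better capture would inform wider use without the exclusions.* Anticoagulant and antiplatelet users, people with bleeding disorders and peri-surgical patients are not studied, so no question put to the others answers for them.

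**Conclusion.** The point holds as a low-cost improvement of minor priority. For a risk the protocol names and acts on, the plan has no directed question, conflicting rules on recording non-serious unrelated events, and no pooled summary. The loss is confined to minor bleeds that patients do not mention or that stay off the eCRF as unrelated; for these, no later grouping of terms helps.

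The size is a looser bound and a smaller recorded difference. A zero count excludes rates above 2.7% (n = 108) or 3.2% (n = 91) only if capture is complete. The 5.5% and 11% figures for n = 108 rest on assumed capture of one half and one quarter and show direction, not a measured loss. Repairing capture and tabulation gives a more complete estimate with a confidence interval, not a causal answer.

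**What to change.** - Keep the open AE question. After it, add one scripted question on bleeding or unusual bruising at the Day 3, 7, 10 and 14 calls.
- Reconcile Protocol Appendix B 4.2 with Protocol 5.2.1.2 and SAP 5.1, so that every bleeding event goes into the eCRF whatever its judged causality.
- In SAP 6.5.2.1 and the section 7 table list, add one pre-specified row, *any treatment-emergent bleeding event*, by arm with the risk difference and 95% CI. Define the grouped terms before database lock and label the row descriptive.

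The cost is one line in the phone script, one recording rule and one table row. The downside is more minor events recorded in both arms. The question helps only patients still to be called; the row can be added at any time before database lock, using whatever has been recorded. Nothing here changes a dose or a clinical rule.
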